## 10.PLANNED STATISTICAL METHODS

### 10.1. Statistical Considerations

#### 10.1.1. General definitions

In all applicable summary/analysis presentations of safety endpoints, Baseline is defined as the last non-missing assessment value for a subject, for that particular parameter, that is prior to dosing with UPB-101 or placebo on Day 1 (including unscheduled assessments), unless over-ruled after review of data at the BDRM or otherwise stated in the appropriate endpoint sections below.

For efficacy endpoints, the baseline definition is as per the appropriate endpoint sections below. For the derivation of most efficacy endpoints, the first assessment to be used should be the first assessment that was taken after the first dose of study treatment.

A subject will be considered to have completed the study after his/her attendance at the last planned study visit (i.e., Week 32 visit), or the last unscheduled visit after the Week 32 visit (if any occur), as applicable.

Within summary presentations/analyses it is envisaged that only scheduled protocol visit values will be used for post-baseline time points. In the clinical database a number of data points have been labelled as unscheduled/additional recordings of data. These data points will be included within subject listings only. However, at the BDRM the occurrence of such unscheduled data will be reviewed for each subject to decide if (and how) any such data point(s) should be included within summary presentations/analyses. Any such decisions will be documented in the BDRM minutes.

#### 10.1.2. Administrative Interim Analysis

An administrative interim analysis will be conducted prior to the Final analysis. This analysis is solely for internal decision-making pertaining to matters unrelated to the current study, UPB-CP-01, and so will have no bearing on the continued conduct and/or analysis of the study.

The administrative interim analysis will consist of a selected subset of the TFLs that will be produced for the final study reporting, identified in [Section 13](#).

A separate unblinded team comprising of a statistician and programmers will produce the outputs for the administrative interim analysis. All data and outputs will be kept in a secure folder which is only accessible by the unblinded team for the administrative interim analysis. Since the Sponsor is unblinded, the results may be made available to all Sponsor personnel but not to any CRO or site personnel.

#### 10.1.3. Data Presentation

The full list of TFLs to be produced for the final study analysis are shown in [Section 13](#), and the specific format and content of each data Table/Listing presentation is shown in [Section 14](#).

Summary Tables and Figures will be presented by treatment group (and also for an Overall column including all subjects, for selected data presentations). Within all Tables and Figures values for the treatment groups will be labelled as follows:

- [REDACTED] mg [REDACTED]
- [REDACTED] mg [REDACTED]

- [REDACTED] mg [REDACTED]
- [REDACTED] mg [REDACTED]
- Placebo and/or
- Screen Failures

An Overall column may be included in the disposition, and selected safety outputs which will include all treatment groups (Active and Placebo). Generally, the placebo groups will be pooled across all cohorts however, for some summaries placebo may be summarized according to dosing regimen (e.g. Placebo [REDACTED], Placebo [REDACTED] ) or treatment group (e.g. Placebo [REDACTED]).

For screen failures, data is only expected in a selection of datasets. The data collected within these datasets will be included in the relevant listings only. Additional data that may have been collected for screen failures, in error, will not be displayed in the participants listings. They will not be included in any summary tables.

For selected outputs the dosing regimen may be used in the summaries where cohorts of the same dosing regimen (i.e. [REDACTED], [REDACTED] ) will be grouped together, similarly cohorts may be grouped together by treatment group if there are multiple cohorts with the treatment group (e.g. [REDACTED] [REDACTED]), or summaries may be produced combining all of the active groups together. The ordering of treatment groups shown here represents the order in which they will appear in outputs.

The scheduled protocol visits will be labelled in (applicable) report presentations as follows:

- Screening: Visit 1
- Screening: Visit 2
- Screening: Visit 3
- Day 1
- Day X (where X is the protocol specified Day, to be included within summary Table)
- Week X (where X is the protocol specified study Week, to be included within summary Table)

Generally, the summaries will be produced by Day, although in some cases it may be preferable to summarize by Week. This will be specified within each of the shells, as appropriate.

Note that the Baseline label will be used in some summaries, where Baseline will consist of data collected at the screening visits, on Day 1 pre-dosing or unscheduled assessments prior to dosing (if they are the last non-missing assessment). The actual Baseline definition will be provided in the section relevant for each endpoint.

Unscheduled visit data will be labelled as “Unscheduled” together with a date in data Listings. Unscheduled data will not be used in the summary tables unless otherwise agreed at the BDRM.

Where duplicate information is collected in both the database and in the vendor data transfer(s) (e.g., sampling date and time) this information will be reconciled by data management and then the information from the database will be included in subject Listings.

All variables will be listed to the same number of decimal places as reported. Descriptive statistics for all endpoints that are continuous data will have the following summary statistics presented in the following order: n, (arithmetic) mean (rounded to one more decimal place than recorded), geometric mean (for pre-specified endpoints only; rounded to one more decimal place than recorded), standard

deviation (rounded to two more decimal places than recorded), geometric standard deviation (for pre-specified endpoints only; rounded to two more decimal places than recorded), standard error (for pre-specified endpoints only; rounded to two more decimal places than recorded), median (rounded to one more decimal place than recorded), lower and upper quartiles (rounded to one more decimal place than recorded), minimum (as recorded), and maximum (as recorded).

Note: for endpoint(s) that require a geometric mean to be produced, and those endpoint(s) can have raw values of 0 (zero), the geometric mean calculation will add an appropriate constant value to all raw values prior to logging and will subtract that constant value from the final calculated anti-logged mean. The constant value used will be documented in the footnote of the tables. An example of such a calculation is shown below:

Geometric Mean = anti-log {mean (logged (base 10) endpoint values + 1)} - 1

Categorical variables will be summarized using proportions (counts and percentages). The specific approach to calculating percentages (relevant denominator) is detailed within each (relevant) Table template ([Section 14](#)).

Unless otherwise stated in the appropriate endpoint section(s) below, laboratory/efficacy parameter values that are below the level of quantification (BLQ), or less than the lower limit of quantification (<LLOQ) will be set to zero in computations for summary presentations and analysis but will be noted as below the limit of quantification in subject Listings.

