3.8 Unscheduled Visit and Early Termination Visit

Repeat assessments, if needed, will be captured as unscheduled visits if repeated on a separate day.

Early Termination Visits will be captured as unscheduled visits. The assessments conducted at the Early Termination Visit are the same as those conducted at the Final Visit of the Observation Period.

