5.9 Stopping Criteria

5.9.1 Study Stopping Criteria

If any of the following events develop during the study, at any dose of UPB-101, and these events are considered by the Investigator and/or Sponsor to be at least probably related to the administration of UPB-101, an *ad hoc* SRC meeting will be called immediately to investigate the event and to provide a recommendation for stopping or continuing the study or modifying the protocol:

- One or more subjects develop an SAE.
- Two or more subjects in the same cohort develop severe non-serious AEs, independent of within or not within the same system-organ-class.
- One or more subjects develop elevated plasma concentrations of ALT or AST ≥ 3 -fold the ULN and elevated plasma concentrations of total bilirubin (TBL) ≥ 2 -fold the ULN which is confirmed by repeat testing at least 48 to 72 hours after the initial test.

If the SRC recommends modifying the protocol as a condition for restarting the study, a protocol amendment will be submitted to the relevant regulatory authorities and IEC.

Procedures required prior to restarting a halted study are listed in Section 5.11.

Dose Escalation Stopping Criteria

If any of the following events develop during the study, dose escalation will be halted and the SRC will review the event and make a recommendation to stop dose escalation and/or continue dosing with modifications:

- Two or more subjects administered UPB-101 have an elevated plasma concentration of ALT or AST $\geq 3 \times$ ULN that is considered by the Investigator and/or Sponsor related to the investigational product and is confirmed by repeat testing 48 to 72 hours after the initial test.
- Two or more subjects administered UPB-101 have an elevated plasma concentration of TBL $\geq 2 \times$ ULN that is considered by the Investigator and/or Sponsor related to the investigational product and is confirmed by repeat testing 48 to 72 hours after the initial test.
- For additional information on hepatic parameter abnormalities, refer to Appendix 1, Liver Safety Monitoring and Assessment.
- One or more subjects administered UPB-101 has prolongation of QTcF, defined as QTcF >500 ms or >60 ms change from Baseline, that, on multiple ECGs, persists for at least 30 minutes and is considered by the Investigator and/or Sponsor related to the investigational product.
- Pharmacokinetic Stopping Rules – see Section 5.10.

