12 APPENDICES

Appendix 1 Liver Safety Monitoring and Assessment

Any subject enrolled in a clinical study with active drug therapy that reveals an increase of serum aminotransferases $\geq 3 \times$ ULN or bilirubin $\geq 2 \times$ ULN should undergo detailed testing for liver enzymes using the study Chemistry panel defined in Table 10 which includes ALT, AST, alkaline phosphatase (ALP) and TBL. Testing should be repeated within 48 to 72 hours of notification of the test results. For studies for which a central laboratory is used, alerts will be generated by the central laboratory to inform the Investigator, Sponsor's Medical Monitor, and study team when ALT, AST or TBL exceed the thresholds above. Subjects should be asked if they have any symptoms suggestive of hepatobiliary dysfunction.

Definition of Liver Abnormalities

Confirmed abnormalities will be characterized as moderate or severe by the Investigator where ULN:

	ALT or AST	TBL
Moderate	$>3 \times$ ULN	or
Severe†	$>3 \times$ ULN	and

† Hy's Law Definition: Drug-induced jaundice caused by hepatocellular injury, without a significant obstructive component, has a high rate of bad outcomes, from 10% to 50% mortality (or transplant). The 2 “requirements” for Hy’s Law are:

- Evidence that a drug can cause hepatocellular-type injury, generally shown by an increase in transaminase elevations higher than $3 \times$ ULN (“ $2 \times$ ULN elevations are too common in treated and untreated subjects to be discriminating”).
- Cases of increased bilirubin (at least $2 \times$ ULN) with concurrent transaminase elevations at least $3 \times$ ULN and no evidence of intra- or extra-hepatic bilirubin obstruction (elevated ALP) or Gilbert’s syndrome (Temple 2006).

In addition, the subject should be considered to have severe hepatic abnormalities for any of the following:

- ALT or AST $>8 \times$ ULN.
- ALT or AST $>5 \times$ ULN for more than 2 weeks.
- ALT or AST $>3 \times$ ULN and International Normalized Ratio (INR) >1.5 (If INR testing is applicable/evaluated).

- ALT or AST $>3 \times$ ULN with the appearance of fatigue, nausea, vomiting, right upper quadrant pain or tenderness, fever, rash and/or eosinophilia ($>5\%$).

The Investigator may determine that abnormal liver test results, other than as described above, may qualify as moderate or severe abnormalities, and require additional monitoring and follow-up.

Follow-up Procedures

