Confirmed moderate and severe abnormalities in hepatic functions should be thoroughly characterized by obtaining appropriate expert consultations, detailed pertinent history, physical examination and laboratory tests. The Investigator or designee should complete the liver abnormality case report form (LA-CRF) that has been developed globally and can be activated for any study or another appropriate document (e.g., liver abnormality source consistent with the LA-CRF content). Subjects with confirmed abnormal liver test results should be followed up as described below.

Confirmed moderately abnormal liver tests should be repeated 2 to 3 times weekly then weekly or less if abnormalities stabilize or the study drug has been discontinued and the subject is asymptomatic.

Severe hepatic function abnormalities as defined above, in the absence of another aetiology, may be considered an important medical event and may be reported as an SAE. The Sponsor should be contacted and informed of all subjects for whom severe hepatic liver function abnormalities possibly attributable to study drug are observed.

To further assess abnormal hepatic laboratory findings, the Investigator is expected to:

- Obtain a more detailed history of symptoms and prior or concurrent diseases. Symptoms and new-onset diseases should be recorded as “AEs” on the AE page. Illnesses and conditions such as hypotensive events and decompensated cardiac disease that may lead to secondary liver abnormalities should be noted. Non-alcoholic steatohepatitis is seen in obese hyperlipoproteinemic and/or diabetic subjects, and may be associated with fluctuating aminotransferase levels. The Investigator should ensure that the medical history documentation captures any illness that predates clinical study enrolment that may be relevant in assessing hepatic function.
- Obtain a history of concomitant drug use (including non-prescription medications, complementary and alternative medications), alcohol use, recreational drug use, and special diets. Medications, including dose, should be entered on the concomitant medication page. Information on alcohol, other substance use, and diet should be entered on the LA-CRF or an appropriate document (e.g., liver abnormality page from the source).
- Obtain a history of exposure to environmental chemical agents.
- Based on the subject’s history, other testing may be appropriate including:

- Acute viral hepatitis (A, B, C, D, E or other infectious agents).

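### By the SAP's default, Early Termination results and separate-day repeats stay out of the by-visit laboratory, vital-sign and ECG tables, and the exceptions have no stated criteria

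*SAP*

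**What the plan says.** **Capture.** Protocol 3.8 states "Early Termination Visits will be captured as unscheduled visits" and "Repeat assessments, if needed, will be captured as unscheduled visits if repeated on a separate day". The ET visit has the same content as the Final Visit.

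**Default for tables.** In SAP 10.1.1, "it is envisaged that only scheduled protocol visit values will be used for post-baseline time points", and unscheduled points go to listings. SAP 10.1.3 repeats this: "Unscheduled data will not be used in the summary tables unless otherwise agreed at the BDRM". The BDRM looks at such data subject by subject, settles whether and in what way they are tabulated, and minutes its decision. Neither section gives criteria. Unscheduled values taken before the first dose can still serve as baseline, so the default bites only after baseline.

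**Tables.** SAP 10.12.3, 10.12.4 and 10.12.6 describe the laboratory, shift, vital-sign and QTc tables by visit or time point, and none of them overrides the default. This matches Protocol 9.4.6, which asks for by-visit summaries, and Protocol 9.4.1, which analyses by nominal visit without windows. The table list in SAP 13.2 names no worst-value table. The Section 14 shells are not in the text available.

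**Retests.** For the combined liver criterion, Protocol 5.9.1 requires an elevation "which is confirmed by repeat testing at least 48 to 72 hours after the initial test". Appendix 1 says "Testing should be repeated within 48 to 72 hours of notification of the test results" and then "Confirmed moderately abnormal liver tests should be repeated 2 to 3 times weekly then weekly or less if abnormalities stabilize". Protocol 3.3 also allows an invalid assessment to be repeated.

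**The last visit of an early leaver.** Protocol 3.1.2 has subjects who withdraw consent attend the Final Visit, and Protocol 5.4.3 and 5.4.4 speak of a combined Final/Early Termination Visit. Protocol 3.8 makes the ET visit an unscheduled one.

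**The concern.** Laboratory, vital-sign and ECG results through Week 24 belong to the primary endpoint (Protocol 2). The study tests nothing, so the summary tables are the main presentation of that endpoint. Protocol 3.9 asks for an ET visit so that final safety data are obtained, yet by default those data enter none of these tables. The same holds for a valid result that replaces a spoiled sample on another day, and for a liver value that peaks between scheduled draws.

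An omitted value enters only through a decision taken after all subjects have finished, without a stated standard. Two meetings could treat the same kind of value differently, and a reader of the tables could not tell which values had been left out.

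**Working it through.** The documents give no figure on this point, so there is none to reproduce. The check sets the rules against the visit schedules.

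**Step 1: which results are affected.** An ET visit is unscheduled (Protocol 3.8), unscheduled post-baseline values stay in listings (SAP 10.1.1, 10.1.3), and no analysis window maps them to a visit (Protocol 9.4.1). ET values are therefore untabulated by default. The same chain applies to repeats on another day. Subjects who stop study drug but stay in the study keep scheduled visits (Protocol 3.9, 4.9.2) and are unaffected.

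**Step 2: early leavers, chemistry** (Protocol Tables 5, 6 and 8).
- Cohorts 1 and 2: post-baseline draws on Day 15 and on Days 29, 36, 57, 71, 85, 113, 141 and 225, so 1 + 8 = 9.
- Spacing inside the Week 24 window: 113 − 85 = 28 and 141 − 113 = 28 days. No chemistry is planned from Day 141 to Day 169 (Week 24), again 28 days.
- Cohorts 3 and 4: 57 − 29 = 28 and 85 − 57 = 28 days.
- An ET result can thus be about 4 weeks later than the subject's last tabulated value.
- After Day 141 in Cohorts 1 and 2, no chemistry, urinalysis or ECG is planned until Day 225: 225 − 141 = 84 days. Completers share this gap, but for a leaver the ET result is the only one due after Day 141.
- Coagulation is planned only at Visit 1 and the Final Visit, so a leaver contributes 0 of 1 planned post-baseline values. Day 225 is after Week 24, so this mainly concerns the exploratory 32-week endpoint.

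**Step 3: liver retests.** Take an abnormality first seen on Day 113 in Cohort 1 or 2. The next planned draw is Day 141, 28 days or 4 weeks later. The retests in between number 1 if only confirmation is done. They number 2 × 4 = 8 to 3 × 4 = 12 if testing stays at 2 to 3 per week throughout, which is an assumption, because Appendix 1 reduces the frequency once values stabilise. By default none of these enters a table. For the analyte that triggered the retest, the shift table already shows a value above range at Day 113. What is lost is the size of a later peak, that is, the maximum in Table 14.3.4.1.

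**Step 4: how many subjects.** No dropout or retest rate is given. One leaver is 1/6 = 16.7% of an active cohort. With an assumed rate d of early leaving, the chance of at least one leaver among 6 is 1 − (1 − d)^6: 26.5% for d = 5%, 46.9% for 10% and 73.8% for 20%. The true number may be zero.

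**Step 5: a side effect of worst-value rows.** Planned post-baseline haematology draws are 2 + 10 = 12 in Cohorts 1 and 2, 2 + 8 = 10 in Cohort 3, and 4 + 8 + 4 = 16 in Cohort 4. Assume a 2.5% chance that any one value is above range. If values are independent, the chance of at least one is:
- 1 − 0.975^12 = 26.2% (Cohorts 1 and 2)
- 1 − 0.975^10 = 22.4% (Cohort 3)
- 1 − 0.975^16 = 33.3% (Cohort 4)

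If values within a subject are fully correlated, it is 2.5% in every cohort. This measures a drawback of the remedy, not the size of the problem.

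**The case against.** The SAP does state a rule, twice, and the exception runs through a blinded, minuted meeting before final lock. The by-visit tables are what Protocol 9.4.6 asks for, and no passage promises a worst-value or ET row. That stands: the tables do not contradict the protocol, and only the criteria for exceptions are missing.

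Liver peaks that matter are handled in other ways. Appendix 1 provides a dedicated case report form, expert consultation and possible SAE reporting, and Protocol 5.9.1 brings the safety committee in when a criterion is met. In cohorts of 6 + 2, a listing and a narrative may say more than a table maximum. This also stands, and it limits the harm. It does not put the value into the table that summarises the endpoint.

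The case is thinner for ECG and vital signs. The only separate-day retest schedule that the protocol directs is for liver tests. The QTc criterion in Protocol 5.9.1 concerns persistence over at least 30 minutes; same-day repeats fall outside Protocol 3.8, and SAP 10.12.6 averages three or more tracings. For these measures the ET visit is the main case.

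Finally, the unseen Section 14 shells might already contain such rows. That cannot be excluded, but neither the method sections nor the table titles suggest it.

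**Conclusion.** The point holds in this form: the stated default, followed exactly, omits complete withdrawers' ET results, valid separate-day replacements and retest-only liver peaks from the by-visit safety tables, and the route for exceptions has no criteria. Separately, Protocol 3.1.2, 5.4.3 and 5.4.4 blur or conflict with the capture rule in Protocol 3.8. If an early leaver's last visit were recorded as the Final Visit, its results could be tabulated as Day 225.

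Severity is minor to moderate. All values are listed, clinically significant laboratory abnormalities become AEs (Protocol 8.8), AE tables work by date (SAP 10.12.2), and nothing is tested (SAP 10.1.4). The conclusion rests on Protocol 3.8 governing data capture and on the shells adding no further rows.

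A reader might infer three stronger things that the documents do not support:
- **That safety data are lost from the report.** They are listed in full; the loss is from the tables.
- **That the unblinded Sponsor can steer inclusion.** No passage places Sponsor staff at the BDRM, and SAP 4 requires their involvement in SAP changes beyond the first draft to be documented.
- **That the tables favour the drug.** An omitted value can be normal or abnormal, in either arm, so the direction of any bias is unknown.

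**What to change.** 1. Reconcile Protocol 3.1.2, 5.4.3 and 5.4.4 with Protocol 3.8, so that an early leaver's last visit is recorded as ET and not tabulated as Day 225.
2. In SAP 10.1.1 and 10.1.3, keep the by-visit tables on scheduled nominal visits and add a separate ET row, not mapped to any visit, to the safety laboratory, vital-sign and ECG tables.
3. Add worst post-baseline rows (any value above range, any value below range) to Tables 14.3.3.2, 14.3.4.2 and 14.3.5.2. Add a maximum post-baseline row for ALT, AST and total bilirubin to Table 14.3.4.1, because a shift row cannot show the size of a peak, and a maximum post-baseline row to QTc Table 14.3.8.3. Use all valid scheduled, unscheduled and ET values, in active and placebo alike, through Week 24 (same cut-off as the AE tables) and for the whole study. Print the number of assessments per group beside each row.
4. Limit the BDRM to judging whether an individual value is valid, for example after a haemolysed sample.

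The cost is SAP wording, a few table rows and a small clarification in the protocol; no new data are collected. There are two downsides. ET rows will have small n. Worst-value rows will show more abnormalities where more samples are taken, which is why the assessment counts are needed.
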